7.3.2. Afib Classification Accuracy Calculations

Classification accuracy will be measured by Sensitivity and Specificity as defined below.

Test \ Reference	AFIB	No AFIB
AFIB	TP	FP
No AFIB	FN	TN

$$Sensitivity = \frac{TP}{TP + FN}$$

$$FalseAlarmRate = 1 - Specificity = \frac{FP}{FP + TN} = \frac{FP}{TotalNegativeEvents}$$

$$PPV = \frac{FP}{TP + FP} = \frac{FP}{TotalPositiveDetections}$$

$$Accuracy = \frac{TP + TN}{TP + FP + FN + TN}$$

Analysis methods consistent with Receiver Operating Characteristics (ROC) curves will be used.

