6. DESIGN OF THE CLINICAL INVESTIGATION

6.1. General

This is a prospective, nonrandomized, single arm study. The study endpoints are designed to validate the performance of Masimo INVSENSOR00057 in detecting Afib. The validation of the Afib detection function in the investigational device may be determined using data collected from this study, in addition to data from other Masimo sponsored studies.

The primary endpoint of this study will be the analysis of sensitivity and specificity of Masimo INVSENSOR00057 Afib detection function when compared to data collected using an FDA-cleared ECG monitor.

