7. STATISTICAL DESIGN AND ANALYSIS

7.1. Acceptance Criteria

For validation studies, acceptance criteria are determined by Masimo specifications.

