7.2. Sample Size

Analysis methods consistent with Receiver Operating Characteristics (ROC) curves will be used. Therefore, the sample size was determined to meet simultaneous requirements for both Sensitivity and Specificity. The PASS 2019 software package was used to calculate the appropriate sample size using the Confidence Intervals for One-Sample Sensitivity and Specificity module. [REDACTED]

[REDACTED]

[REDACTED]

[REDACTED]

[REDACTED]

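### The PPV formula in Section 7.3.2 has FP in the numerator, so it computes 1 − PPV; both printed forms need TP

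*Combined protocol and SAP*

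**What the plan says.** Section 7.3.2 sets out a two-by-two table with the test result in the rows and the reference in the columns. The test-AF row contains TP and FP; the test-no-AF row contains FN and TN. Four formulas follow:

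- Sensitivity: "Sensitivity = \frac{TP}{TP + FN"
- False alarm rate: "FalseAlarmRate = 1 - Specificity = \frac{FP}{FP + TN} = \frac{FP}{TotalNegativeEvents"
- PPV: "PPV = \frac{FP}{TP + FP} = \frac{FP}{TotalPositiveDetections"
- Accuracy: "Accuracy = \frac{TP + TN}{TP + FP + FN + TN"

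The sentence introducing them names only two measures: "Classification accuracy will be measured by Sensitivity and Specificity as defined below". Section 6.1 is consistent with that: "The primary endpoint of this study will be the analysis of sensitivity and specificity of Masimo INVSENSOR00057 Afib detection function". PPV appears nowhere else in the visible text. Section 7.1 gives no numerical criterion for any measure; it says that "acceptance criteria are determined by Masimo specifications".

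**The concern.** PPV is the proportion of positive detections that the reference confirms, so the confirmed detections (TP) belong in the numerator. The plan puts the unconfirmed ones (FP) there, in both forms of the expression. The denominators are right, so the result is a legitimate quantity under the wrong name: the false discovery proportion.

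This is a definition in the statistical analysis section, not background text. An analyst who codes it as written would report the complement of PPV under a standard label, and good performance would look poor. An analyst who corrects it silently would depart from the written plan. Section 17 says the results will be made public, so a wrong value could leave the sponsor's files.

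**Working it through.** **Inputs.** The cell labels and the four formulas come from Section 7.3.2. The documents give no numerical PPV to reproduce, and no expected sensitivity, specificity or record counts are visible. The algebra needs none of these; the numerical illustrations rest on assumed counts.

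**Step 1: algebra.** Total positive detections = TP + FP (the test-AF row).

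- Correct: PPV = TP/(TP + FP)
- Printed: FP/(TP + FP)
- Sum: (TP + FP)/(TP + FP) = 1, so printed = 1 − PPV

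The two are equal only if FP = TP, when both are 50%.

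**Step 2: could the labels explain it?** Sensitivity as TP/(TP + FN), false alarm rate as FP/(FP + TN) and accuracy as (TP + TN)/(TP + FP + FN + TN) all match the table as labelled, so the labels are not swapped. Transposing the table does not help either: the numerator of PPV is the cell in which test and reference both show AF, and that cell is TP in either orientation.

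**Step 3: size.** Let TP = sensitivity × AF records and FP = (1 − specificity) × non-AF records. With an assumed 100 AF and 100 non-AF records:

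| Sensitivity | Specificity | TP | FP | Printed: FP/(TP + FP) | Correct: TP/(TP + FP) |
|---|---|---|---|---|---|
| 100% | 100% | 100 | 0 | 0/100 = 0% | 100/100 = 100% |
| 95% | 95% | 95 | 5 | 5/100 = 5.0% | 95/100 = 95.0% |
| 95% | 90% | 95 | 10 | 10/105 = 9.5% | 95/105 = 90.5% |
| 95% | 80% | 95 | 20 | 20/115 = 17.4% | 95/115 = 82.6% |
| 80% | 95% | 80 | 5 | 5/85 = 5.9% | 80/85 = 94.1% |

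Rows 2 to 4 show the printed value rising as specificity falls. Rows 2 and 5 show it rising as sensitivity falls.

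**Step 4: case mix.** PPV depends on the ratio of AF to non-AF records, so that assumption is varied too. Hold sensitivity and specificity at 95% and AF records at 100 (TP = 95):

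| Non-AF records | FP | Printed | Correct |
|---|---|---|---|
| 0 | 0 | 0/95 = 0% | 95/95 = 100% |
| 20 | 1 | 1/96 = 1.0% | 95/96 = 99.0% |
| 100 | 5 | 5/100 = 5.0% | 95/100 = 95.0% |
| 300 | 15 | 15/110 = 13.6% | 95/110 = 86.4% |
| 1,900 | 95 | 95/190 = 50% | 95/190 = 50% |

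The percentages change with the mix, but the two columns always add to 100%.

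**The case against.** The algebra is hard to contest. The case on the other side is about consequence, illustration and source.

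- **Consequence.** PPV is not an endpoint, is not among the measures that Section 7.3.2 says it will use, and has no visible threshold. The visible sample-size text in Section 7.2 also concerns only the two primary measures: "The PASS 2019 software package was used to calculate the appropriate sample size using the Confidence Intervals for One-Sample Sensitivity and Specificity module". A PPV near 0% beside high sensitivity and specificity would probably be noticed. All of this stands, and it keeps the point a minor one.
- **Illustration.** Section 6.3 enrols only subjects with confirmed active AF, and Section 7.3.1 removes those whose waveforms do not fit that diagnosis. On the visible text, non-AF records would have to come from other sponsor studies, which Section 6.1 allows, or from something in the redacted text. The 100/100 mix therefore does not describe this study's own sample. That is fair, but it does not rescue the formula. With no non-AF records FP is 0, and the printed formula returns 0% for any device with at least one true detection, where the correct form returns 100%.
- **Source.** The line above it, for the false alarm rate, also has two fractions with FP in both numerators. Carry-over from that line could account for both errors, either as an author's copy-and-paste (a real error) or as a misreading when the equations were converted from PDF (not an error in the plan). Nothing visible points to a misreading, and the denominators changed correctly, but the possibility justifies looking at the PDF before raising the point.

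**Conclusion.** The concern holds. On the plan's own table the printed PPV is exactly 1 − PPV, at any counts and any case mix; it coincides with PPV only when TP = FP. In the illustrations it gives 0% for a perfect device, and 5.0% to 17.4% where PPV is 95.0% to 82.6%. Those percentages rest on assumed counts; the identity does not. The conclusion does not depend on redacted material and assumes only that the text matches the source PDF.

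This should be fixed, but it does not threaten the primary result. The printed formulas for sensitivity and for 1 − specificity are correct, and no visible decision rule uses PPV.

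**What to change.** Check the line against the source PDF. If it reads as shown here, replace both forms in Section 7.3.2 with PPV = TP/(TP + FP) = TP/TotalPositiveDetections. If any analysis code has already been written from this section, check its PPV line as well.

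The cost is one formula line in an amendment. The sample, data collection and primary endpoint do not change.

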3. JUSTIFICATION FOR THE DESIGN OF THE CLINICAL INVESTIGATION

There are an estimated 46 million individuals suffering from atrial fibrillation, the most common type of cardiac arrhythmia characterized by high frequency of the atrium. Patients with atrial fibrillation have approximately a 4-fold increased risk of mortality compared to the general population (Lee et al., 2018). In addition to increased risk of death, atrial fibrillation also

increases risk of heart failure and stroke. The imminent risks of stroke can be mitigated with prompt administration of anticoagulants (Piazza et al., 2018).

Certain populations are more vulnerable to atrial fibrillation than others; studies have indicated that risk factors for increased risk include older age, sedentary lifestyle, obesity, smoking, diabetes mellitus, hypertension, and obstructive sleep apnea (Staerk et al., 2018). Detecting atrial fibrillation in its early stages can significantly reduce the high disability and mortality rate. A study reviewing the prevalence of atrial fibrillation in 2009 estimated that 700,000 cases were undetected, comprising 13.1% of all cases; half of these projected cases of undiagnosed atrial fibrillation were at increased susceptibility to stroke (Turakhia et. al, 2018).

The intent of this study is to validate the performance of Masimo INVSENSOR00057 in detecting atrial fibrillation. The standard for diagnosis of atrial fibrillation is use of an electrocardiogram (ECG); advancement of this technology, especially via wearable technology, for early detection can improve the prognosis for patients and enable them to seek medical care before the arrhythmia progresses into more adverse complications.

4. BENEFITS AND RISKS OF THE INVESTIGATIONAL DEVICE, CLINICAL PROCEDURE, AND CLINICAL INVESTIGATION

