6.3. Subjects

Inclusion Criteria

- Subject is 18 years of age or older.
- Subject is confirmed to have active atrial fibrillation at the time of enrollment.

Exclusion Criteria

- Subject is confirmed to have concurrent active arrhythmias (e.g., PVCs, bradycardia, etc.) at the time of enrollment.
- Subject is allergic to adhesives or ECG gel.
- Subject whose skin is not intact in or at the vicinity of the device placement site.

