6.4. Procedures

6.4.1. Recruitment and Pre-Screening

Subjects will be recruited from local clinics or cardiology offices. Subjects who present with active atrial fibrillation during their regular doctor visit will be recruited for the study.

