7.3. Statistical Analysis**7.3.1. Exclusion**

The following subjects will be excluded from data analysis:

- Subjects where the paired reference or test ECG did not provide readable ECG waveforms as determined by medical personnel.
- Subjects who presented as having Afib at the time of enrollment, but who provided ECG waveforms with characteristics inconsistent with an Afib diagnosis (as determined by medical personnel).

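### Raw-count PPV and Accuracy in section 7.3.2 carry no information beyond sensitivity in an all-AF sample, and with added negatives PPV would follow the mix assembled

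*Combined protocol and SAP*

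**What the plan says.** Section 7.3.2 sets out a two-by-two table of device result against reference and names sensitivity and specificity as the measures of classification accuracy. It then lists formulas for PPV and for Accuracy, the latter as "Accuracy = \frac{TP + TN}{TP + FP + FN + TN}". Both use raw counts. No prevalence term, target prevalence or limit on interpretation is visible.

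Four other places fix the share of AF in those counts:

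- Section 6.3, inclusion: "Subject is confirmed to have active atrial fibrillation at the time of enrollment".
- Section 6.4.1, recruitment: "Subjects who present with active atrial fibrillation during their regular doctor visit will be recruited for the study".
- Section 6.1, design: "This is a prospective, nonrandomized, single arm study".
- Section 7.3.1, which removes from analysis "Subjects who presented as having Afib at the time of enrollment, but who provided ECG waveforms with characteristics inconsistent with an Afib diagnosis".

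Section 6.1 also allows validation to draw on this study's data "in addition to data from other Masimo sponsored studies", without giving their number or AF share. On endpoints it says: "The primary endpoint of this study will be the analysis of sensitivity and specificity of Masimo INVSENSOR00057 Afib detection function". PPV and Accuracy are not named there or in the synopsis.

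**The concern.** PPV depends on the proportion of true AF among those tested, and so does Accuracy unless sensitivity and specificity are equal. Here recruitment sets that proportion, and it says nothing about the people who would wear the device. Section 3 gives the purpose as early detection: "advancement of this technology, especially via wearable technology, for early detection can improve the prognosis for patients". For a wearer who receives an alert, PPV is the natural figure to ask for, and a value from this sample cannot answer that question.

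This is separate from the misprint in the PPV line, where FP stands in the numerator. On an all-AF sample the printed formula returns 0, which would be noticed. Replacing FP with TP returns 100%, which looks plausible and is just as uninformative. The correction of the misprint should therefore not be made alone.

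**Working it through.** **Inputs.** From the documents: about 100 subjects (synopsis); AF share p of about 1 (6.1, 6.3, 6.4.1, 7.3.1); raw-count formulas (7.3.2). Assumed, because the visible text gives no values: sensitivity Se, specificity Sp, the number of added controls, and AF prevalence among users. There is no planned PPV or Accuracy figure to reproduce. The inputs to the sample size in 7.2 are blacked out, so that figure cannot be reproduced either; this is not a fault in the plan.

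**Formulas.** With the numerator corrected, the count definitions in terms of p are:

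- PPV = Se·p / [Se·p + (1 − Sp)(1 − p)]
- Accuracy = Se·p + Sp·(1 − p)

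**Step 1: the plan as written, p = 1.** FP = TN = 0.

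- Printed PPV = 0/(TP + 0) = 0.
- Corrected PPV = TP/(TP + 0) = 1 for any device with TP of at least 1.
- Accuracy = TP/(TP + FN), which is sensitivity, whatever the specificity.

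This step needs no assumption about Se, Sp or prevalence among users.

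**Step 2: controls added to 100 AF subjects, Se = Sp = 0.95.** TP = 95 and FP = 0.05 × controls.

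| Controls | FP | PPV = 95/(95 + FP) |
|---|---|---|
| 25 | 1.25 | 0.987 |
| 50 | 2.5 | 0.974 |
| 100 | 5 | 0.950 |
| 200 | 10 | 0.905 |
| 400 | 20 | 0.826 |

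The device is the same in every row; only the mix changes.

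**Step 3: PPV at assumed prevalences among users.** For example, at Se = Sp = 0.95 and p = 0.02, PPV = 0.019/(0.019 + 0.049) = 0.279.

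| Se / Sp | 10% | 5% | 2% | 1% |
|---|---|---|---|---|
| 0.90 / 0.90 | 0.500 | 0.321 | 0.155 | 0.083 |
| 0.95 / 0.95 | 0.679 | 0.500 | 0.279 | 0.161 |
| 0.98 / 0.90 | 0.521 | 0.340 | 0.167 | 0.090 |
| 0.90 / 0.98 | 0.833 | 0.703 | 0.479 | 0.312 |
| 0.98 / 0.99 | 0.916 | 0.838 | 0.667 | 0.497 |

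**Step 4: Accuracy.** It always lies between Se and Sp, and does not move with p when they are equal.

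| Se / Sp | p = 1 | p = 0.50 | p = 0.01 |
|---|---|---|---|
| 0.98 / 0.90 | 0.980 | 0.940 | 0.901 |
| 0.90 / 0.98 | 0.900 | 0.940 | 0.979 |

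The all-AF sample flatters the first device and understates the second.

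**The case against.** The strongest reply is that neither measure carries weight in this study. The endpoints are sensitivity and specificity, 7.3.2 itself says classification accuracy is measured by those two, and no acceptance criterion is visibly tied to PPV or Accuracy. That stands, and it makes this a secondary reporting point.

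A reader might infer that the sponsor intends to present PPV as performance in users, or that most alerts in use would be false. The documents support neither. They do not say how PPV will be presented, and they give no prevalence among users; at an assumed 10% with Se = Sp = 0.95, about two alerts in three are true (0.679).

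It can also be said that the result at p = 1 follows from a more basic gap, the absence of reference-negative subjects. That is so, but Step 2 shows that filling the gap does not make the raw-count PPV meaningful for users. Whether outside data would enter the 7.3.2 counts is not stated; section 6.1 says only that they may contribute to validation, so Step 2 is conditional.

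Last, parts of 6.4.3 and 7.2 are blacked out, 7.4 refers to groups although the design has one arm, and the denominators in 7.3.2 are labelled as events and detections, so the unit may be recordings. These leave the exact counts uncertain. They do not rescue the figures, because any negatives would only move PPV to whatever mix resulted.

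**Conclusion.** The point holds as a secondary matter of reporting and interpretation. With the numerator corrected and the sample as described, PPV is 100% by construction and Accuracy duplicates sensitivity. This rests only on the AF share being about 100%. With negatives added, raw-count PPV would reflect the mix assembled: 0.987 to 0.826 over 25 to 400 controls at assumed Se = Sp = 0.95. The size of the gap to real use rests on assumed prevalences of 1% to 10%, which give 0.16 to 0.68 for the same device.

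Accuracy is the weaker half: it varies only when sensitivity and specificity differ, and in either direction. It would be wrong to conclude from this point that the primary analysis is affected; whether specificity can be estimated without reference-negative subjects is a separate question.

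**What to change.** In 7.3.2, delete PPV and Accuracy as performance measures computed from the study's counts. The acceptable minimum is to keep them, with the PPV numerator corrected, under a statement that they are specific to this sample and will not be cited as performance in users. Either choice is a change of wording, with no added subjects or procedures.

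If a PPV for users is wanted, pre-state a range of prevalences (for example 1%, 2%, 5% and 10%) and report Se·p / [Se·p + (1 − Sp)(1 − p)] at each, with confidence intervals. This is possible only if specificity is available from a stated source of AF-free recordings. The visible design does not supply one, so this option costs more than wording unless suitable data exist. Those recordings should also resemble users: section 6.3 excludes other concurrent arrhythmias, and a specificity estimated under the same exclusion would not by itself give PPV in users. The resulting PPV will be less favourable than 100%, but interpretable.

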7.4. Expected Dropout Rates

Subjects may not complete the study for various reasons, such as a clinical screening test failure, at the investigator's or study staff's discretion, or because the subject does not want to continue the study. Due to the short duration and simple, noninvasive procedures of this study, there are limited expected dropouts.

However, the sample size per group may be increased to account for dropout rates during the study.

8. DATA MANAGEMENT

8.1. Data Management and Confidentiality

All documents associated with this protocol will be securely stored in a physical location or on password-protected computers. The confidentiality and retention of these documents will be protected to the extent provided and required by the law. All data will be de-identified before any statistical analysis. Only de-identified data will be shared with Masimo for research purposes stated in this protocol. Data collected by data capture software and data entered in case report form will be shared with Masimo via a secure, password-protected server that only study staff and Masimo study team members will have access to. Data will be retained for a minimum to 2 years following completion of the final analysis.

8.2. Source Documents

Source data is all information, original records of clinical findings, observations, or other activities in a clinical trial necessary for the reconstruction and evaluation of the trial. Source data are contained in source documents. Examples of these original documents and data records include: hospital records, clinical and office charts, laboratory notes, memoranda, recorded data from automated instruments, and copies or transcriptions certified after verification as being accurate and complete.

8.3. Case Report Forms

The site shall capture study data in case report forms (CRFs) for each subject enrolled, to be provided to the sponsor. CRFs may be in paper or electronic format through electronic data capture (EDC) software. Masimo shall ensure that systems used for electronic CRFs are compliant with the requirements of 21 CFR Part 11 and ISO / IEC 27001 Certification. The CRFs will be completed and signed by the principal investigator or delegate. This also applies to those subjects who fail to complete the study. If a subject withdraws from the study, the reason must be noted on the CRF. Case report forms are to be completed on an ongoing basis. CRF entries and corrections will only be performed by study site staff, authorized by the investigator. For paper CRFs, entries and corrections to the CRF will be made following Good Documentation Practices.

The CRF may include the following information, including but not limited to: inclusion / exclusion criteria, whether subject consent was obtained before start of study, demographic information, device readings, and if occurrence of any adverse event, protocol deviation, and device deficiencies, etc. The CRFs will be signed by the PI or delegate to attest that the data are complete and accurate.

CRF entries will be checked by the study monitor and any errors or inconsistencies will be queried to the site on an ongoing basis. Any changes made within an electronic CRF will be tracked by audit trail. Any changes on a paper CRF will be made directly on the CRF and will be initialed and dated by the person making the change. Query resolution will be assessed and confirmed by study monitor during site visit.

8.4. Data Transfer and Storage

8.4.1. Original paper CRFs will be stored in a secure location at the site. Copy of the original paper CRFs may be scanned and sent to sponsor. If using electronic CRFs, the site staff will be assigned unique usernames and passwords for data

security. Final copies of the electronic CRFs in EDC are stored on a secure server.

- 8.4.2. Only authorized sponsor personnel will have access to study data, and will move it to a secure and backed-up drive at Masimo.
- 8.4.3. CRFs will be checked for completeness and if there are inconsistent or missing data points, queries will be generated. If delegated study staff are to correct the paper CRF, they shall follow GDP practices to strike through old entry, add in new entry, and initial and date it, and provide the corrected information to sponsor. Corrections made to electronic CRFs will be tracked by audit trail and require PI or delegate sign-off.

8.5. Record Retention

Study data will be retained for the necessary period of time as required by the institution's regulations. Study records shall be retained for a minimum of two years after study closure. The Institution's own retention policies and regulations may apply in addition to the minimal requirement.

